### **6.6.4 Prohibited Therapy**

The following medications are prohibited during the study unless stated otherwise.

- Any investigational medication other than the study drug is prohibited. Use of such medications within 30 days or 5 half-lives, whichever is longer, before the first dose of study drug and during the study through the safety follow-up visit is prohibited. Therapies which would typically be prohibited may be administered if necessary to preserve the health or safety of a participant (e.g. vaccines or medical products for prevention or treatment of COVID-19). Principal Investigator and Medical Monitor should be informed of any administration. Administration of these therapies should be avoided immediately prior to ECP
- Addition of any other *new* systemic medications/therapies other than extracorporeal photopheresis to treat chronic GVHD (e.g., calcineurin inhibitors, sirolimus, rituximab, imatinib, etanercept, anti-thymocyte globulin, bortezomib, methotrexate, mycophenolate mofetil, other cytotoxics or immune modulators, other JAK inhibitors, or any investigational agent) is not permitted at any time from screening to the time that INCB039110 therapy is permanently discontinued.

At enrollment, subjects may be receiving other immunosuppressants (e.g., calcineurin inhibitors, sirolimus) for the prophylaxis of GVHD or treatment of acute GVHD. The doses of these medications must have been stable for at least 2 weeks prior to Screening. Adjustments (increases or decreases) to existing immunosuppression are allowed if these adjustments are necessary to maintain a therapeutic drug level. Tapering of immunosuppression is permitted at the provider's discretion and should follow per institutional practice.

If cGVHD develops or worsens during the tapering of existing immunosuppression (e.g., calcineurin inhibitors, sirolimus) for prophylaxis or treatment of aGVHD, the dose of the immunosuppressant may be increased again and will not be considered a treatment failure. A short course of low-dose prednisone (or equivalent)  $\leq 0.5$  mg/kg/d may be considered. Tapering of immunosuppression in this setting should occur after the subject has achieved a treatment response and has withdrawn prednisone (if applicable).

Use of immunosuppression for reasons other than treatment for cGVHD should be discussed with the medical monitor.

- The use of systemic corticosteroid doses of prednisone (or equivalent)  $> 0.5$  mg/kg/day for treatment of acute or chronic GVHD.
  - If a subject requires corticosteroid doses of prednisone (or equivalent)  $> 0.25$  mg/kg/day for the underlying disease or a comorbid condition during study participation, then continuation in the study will be considered on an individual basis by the sponsor and the investigator.
- Subjects receiving itacitinib should avoid consuming pomegranates, pomegranate juice, grapefruits, grapefruit juice, or Seville oranges, all of which are known to inhibit cytochrome CYP3A enzymes and may increase the exposure to itacitinib.

- Coadministration with potent CYP3A4 inducers. The FDA website provides a current list of potent CYP3A4 inducers.
- The use of TPO receptor agonists (romiplostim, eltrombopag) is not permitted from screening to the safety follow-up visit (within the DLT period).
- The use of erythropoietin is not permitted from screening to the safety follow-up visit (within the DLT period).
- Live attenuated vaccines within 28 days prior to the first dose of study treatment and while participating in the study are prohibited. Examples of live vaccines include, but are not limited to: measles, mumps, rubella, chickenpox/zoster, yellow fever, rabies, BCG, and typhoid (oral) vaccine. Seasonal influenza vaccines for injection are generally killed virus vaccines and are allowed; however, intranasal influenza vaccines (e.g., Flu Mist®) are live-attenuated vaccines and are not allowed.
- No surgery (except biopsy), investigational treatment, immunotherapy, or additional chemotherapy is allowed during the course of this study.

## 6.7 Duration of Therapy

In the absence of treatment delays due to an adverse event(s), treatment may continue for 12 cycles (i.e., 12 months) or until criteria for treatment discontinuation are met.

### 6.7.1 Criteria for discontinuation of treatment (“off-treatment”)

Patients may withdraw from treatment or the study overall at any time at their own request, or they may be withdrawn at the discretion of the Investigator for safety, behavioral reasons, or the inability of the patient to comply with the protocol-required schedule of study visits or procedures. In addition to the drug-specific discontinuation criteria listed in Section 6.6, the following will result in treatment discontinuation:

- Subject withdraws consent from the study treatment and/or study procedures. A subject must be removed from the trial at his own request or at the request of his legally acceptable representative. At any time during the trial and without giving reasons, a subject may decline to participate further. The subject will not suffer any disadvantage as a result.
- Treatment failure as defined as:
  - Need for additional systemic therapy for GVHD.
    - If a patient has been tapered off a calcineurin inhibitor or sirolimus used for GVHD prophylaxis at the time of diagnosis of moderate-severe chronic GVHD, reinstatement of the drug will not be considered a failure.
    - Prednisone dose (or prednisone equivalent) used at  $> 0.25$  mg/kg/d for more than 8 weeks or  $> 0.5$  mg/kg/d once will count as a treatment failure, but the participant will be allowed

to remain on the study treatment if deemed to be clinically benefiting by the treating investigator.

- If the participant requires any systemic immunosuppression besides prednisone (i.e., ibrutinib, ruxolitinib, etc.), the participant will be withdrawn from study treatment but remain on study for follow-up.
  - Relapse of primary hematologic disease.
  - Death
- Clinical deterioration that, in the opinion of the investigator, increases the risk to the patient.
- AEs or intercurrent illness that, in the opinion of the investigator, warrants the subject's withdrawal from study treatment.
- Significant noncompliance (defined as missing  $\geq 40\%$  of required study medication) with the protocol schedule or treatment administration in the opinion of the investigator.
- An intercurrent illness that prevents further administration of treatment.
- General or specific changes in the patient's condition render the patient unacceptable for further treatment in the judgment of the investigator.
- Pregnancy.
- Termination of the study by the sponsor.
- The drug manufacturer can no longer provide the study agent.
- Death.

The reason(s) for protocol therapy discontinuation, the reason(s) for study removal, and the corresponding dates must be documented in the Case Report Form (CRF).

#### **6.7.2 Criteria for discontinuation of study ("off study")**

Subjects will be taken off study for the following:

- Completed study follow-up period
- Participant requests to be withdrawn from the study
- If, in the investigator's opinion, the continuation of the trial would be harmful to the subject's well-being.
- Development of intercurrent illness or situation which would, in the judgment of the investigator, significantly affect assessments of clinical status and trial endpoints.
- The subject is lost to follow-up.
- Death.

- Screen failure.

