### **9.5 Follow-up Evaluations**

All patients will be followed for a total of 12 months every 12 weeks ( $\pm 7$  days) after removal from study treatment for GVHD progression, initiation of alternative therapy for GVHD, relapse of the underlying disease, or death. Patients removed from the study for unacceptable adverse event(s) will be followed until resolution or stabilization of the adverse event. For follow-up procedures see the Schedule of Events and the Assessments Section.

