addition of new systemic treatment for chronic GVHD, and use of prednisone dose (or its equivalent) of  $\leq 0.5$  mg/kg/d at 24 weeks. Kaplan-Meier methods will be used for these binary endpoints if there are censored events. Kaplan –Meier methods and associated confidence intervals will be used for survival endpoints (FFS and OS). NRM and RR will be treated as competing risks and analyzed by computing nonparametric subdistribution functions. The minimum, maximum, mean, and median value along with interquartile range will be reported for continuous and ordered categorical endpoints (NIH global score of chronic GVHD, provider, and patient-reported GVHD severity). Change in continuous or ordered categorical endpoints (NIH global score of chronic GVHD, provider, and patient-reported GVHD severity) will be analyzed using paired Wilcoxon tests. The minimum, maximum, mean, and median cumulative prednisone dose at 24 weeks will be reported, along with the interquartile range.

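### Off-study removal for illness or harm under Section 6.7.2 leaves later deaths, relapses and secondary cGVHD therapy without secured follow-up, and no censoring rule covers it, so OS, FFS and NRM could be biased

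*Combined protocol and SAP*

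**What the plan says.** Section 6.7.2 opens with mandatory wording: "Subjects will be taken off study for the following". Two of its criteria turn on the investigator's view of the patient's health. One applies when "the continuation of the trial would be harmful to the subject's well-being". The other reads "Development of intercurrent illness or situation which would, in the judgment of the investigator, significantly affect assessments of clinical status and trial endpoints". Completing the follow-up period is a separate item in the same list, so the natural reading is that the other items end follow-up before it is complete.

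Section 6.7.1 deals with stopping treatment only, and illness appears there too: "An intercurrent illness that prevents further administration of treatment". The same section shows that the protocol can separate the two states, because a patient who needs systemic immunosuppression other than prednisone stops study treatment but is still followed.

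Section 9.5 promises that "All patients will be followed for a total of 12 months every 12 weeks", counted "after removal from study treatment for GVHD progression, initiation of alternative therapy for GVHD, relapse of the underlying disease, or death". Footnote 5 of the Schedule of Events likewise starts survival and disease follow-up when treatment stops. For patients who leave the study, Section 9.5 offers less: "Patients removed from the study for unacceptable adverse event(s) will be followed until resolution or stabilization of the adverse event".

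For the analysis, Section 12.4.2 names Kaplan-Meier for FFS and OS, and nonparametric subdistribution functions for NRM and relapse as competing risks. It gives no censoring rule for any of them. Withdrawal is dealt with explicitly only for the primary endpoint, where it counts as non-response (Section 12.1).

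**The concern.** Kaplan-Meier and cumulative-incidence estimates are valid only if a censored patient has the same outlook as comparable patients still under observation. The two criteria in Section 6.7.2 work against that. One responds to expected harm to the patient, and the other names the expected effect on the endpoints as the reason for removal. Serious illness is a realistic route to death here: Section 3.1.6 lists sepsis and fungal pneumonia among the fatal events in the earlier chronic GVHD study of itacitinib.

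Removal from the study is not an FFS event; the events are secondary therapy, relapse and death (Section 1.2.2). With no rule to the contrary, an analyst would ordinarily censor a removed patient at last contact. If removed patients then do worse than those who stay, OS and FFS are overstated and NRM is understated. The trial has one arm, so there is no control group in which the same bias would occur.

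**Working it through.** **The plan's own figures.** The plan gives no figure for OS, FFS or NRM and no expected rate of off-study removal. The design figures it does give concern the primary endpoint. With boundaries of 7 of 16 and 24 of 46, the probability of rejecting is the sum over x = 8 to 16 of P(X = x) × P(Y ≥ 24 − x), with X ~ Bin(16, p) and Y ~ Bin(30, p). This gives 0.04859 at p = 0.40 and 0.8006 at p = 0.60, which reproduces the stated 0.0486 and 80%. Because withdrawal counts as non-response, off-study removal does not change these error rates.

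**Who is covered after leaving, and for what.**

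| State | Follow-up secured | Source |
|---|---|---|
| Off treatment | 12 months, every 12 weeks, for GVHD progression, new GVHD therapy, relapse, death | 9.5, footnote 5 |
| Off study for an adverse event | Until the event resolves or stabilizes | 9.5 |
| Within 30 days of last dose | Serious adverse events, including fatal ones (collection ends sooner if new cancer treatment starts) | 16.5 |
| Any death that comes to the site's notice | Reporting or eCRF entry, counted from last dose | 16.6 |
| Off study under the two criteria, after those windows | No scheduled contact for death, relapse or secondary therapy | none found |

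The gap is easiest to see in a patient removed at month 2 whose illness stabilizes and who dies at month 8. That death belongs in 1-year OS and may belong in NRM, but no planned contact would find it.

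**Possible size, by illustration.** N = 46 is the planned Part 2 total. Everything else is assumed: D deaths evenly spaced from day 20 to day 340, k of them (spread through the sequence) censored 14 days before death, and no other censoring before day 365. At this spacing no other death falls inside the 14 days, so hiding a death removes its factor (1 − 1/n) from the Kaplan-Meier product and leaves every other factor unchanged, where n is the number at risk at that death. Hence observed OS = true OS × the product of n/(n − 1) over the hidden deaths.

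Example with D = 9: true OS = 37/46 = 80.4%. If the fifth death is hidden, n = 42 and observed OS = 0.8043 × 42/41 = 82.4%. If the third, fifth and seventh are hidden, observed OS = 0.8043 × 44/43 × 42/41 × 40/39 = 86.5%.

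| True deaths D | True 1-year OS | 1 hidden | 2 hidden | 3 hidden |
|---|---|---|---|---|
| 5 | 89.1% | 91.2% | 93.3% | 95.5% |
| 7 | 84.8% | 86.8% | 88.9% | 91.0% |
| 9 | 80.4% | 82.4% | 84.4% | 86.5% |
| 12 | 73.9% | 75.8% | 77.7% | 79.7% |

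One hidden death adds 1.9 to 2.1 points and three add 5.8 to 6.4. If NRM is computed as the simple proportion defined in Section 1.2.2, each unseen non-relapse death lowers it by 1/46 = 2.2 points.

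**The opposite case.** With D = 9, suppose the removed patients would in fact have survived the year, and censor them between days 60 and 200. OS then moves from 80.4% to 80.1% (one removed), 79.9% (two), 79.5% (three) or 79.2% (four). There is no upward bias, only a small shift down.

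**The case against.** A reader might infer that Section 6.7.2 removes any patient who becomes ill, that such patients are censored just before death, and that survival is therefore overstated by 4 to 8 points. The documents do not support that reading, for five reasons.

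- The illness criterion is narrow. It needs a judgment that assessments and endpoints would be significantly affected. Adverse events, clinical deterioration and illness that prevents dosing are reasons to stop treatment in Section 6.7.1, and those patients stay in follow-up.
- Early deaths are largely covered. Section 16.4 follows adverse events to resolution with their outcome, Section 16.5 collects serious events to 30 days after the last dose, and Section 16.6 counts from the last dose rather than from on-study status. A patient dosed until removal who dies of infection two weeks later would normally be captured.
- No passage says that removed patients are censored. That is an inference from the named methods and the absence of a rule.
- Sections 6.7.2 and 9.5 govern different states, so this is a missing link more than a flat contradiction.
- A figure of 4 to 8 points needs two to four of seven deaths to be hidden. The documents give neither count, and the range properly starts at zero or slightly below.

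It is also true that the affected endpoints are secondary, and that the reason and date of study removal go into the CRF (end of Section 6.7.1), so the cases can be identified.

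All of this stands, and it limits the point without removing it. Section 16.6 is a reporting duty: it schedules no contact after removal and does not reach relapse or secondary therapy. A CRF entry shows who was removed, not what happened to them afterwards.

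**Conclusion.** The point holds in a limited form. Followed as written, Section 6.7.2 permits loss to follow-up that may be related to prognosis, for OS, FFS, NRM and relapse, and Section 12.4.2 does not say how such patients are analyzed. Upward bias in OS and FFS, and downward bias in NRM, requires three things together: that patients are removed on these two grounds, that they are censored at removal without later event data, and that removal predicts the event. Under those conditions the illustration gives about 2 points of 1-year OS per hidden death among 46 patients. The number of such deaths cannot be found from the documents and may be zero. The primary endpoint, its error rates and the two-stage decision are not affected. This should be corrected, but it does not threaten the main conclusion of the trial.

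**What to change.** 1. Reconcile Section 6.7.2 with Sections 6.7.1 and 9.5, so that the harm and intercurrent-illness reasons can end study treatment and any burdensome study procedures but do not end follow-up. The well-being criterion need not be deleted; it protects participants, and the change concerns data collection only.
2. State in Section 9.5 that vital status, relapse and start of secondary cGVHD therapy are collected through the full 9.5 period for these patients, unless consent to follow-up is withdrawn or the patient is lost.
3. State the censoring rule for OS, FFS, NRM and relapse in Section 12.4.2.
4. Add a sensitivity analysis that counts illness-related removals as events at the date of removal, using the reasons and dates already in the CRF. It is a pessimistic bound: with 9 true deaths and 3 removed patients who in fact survived, it would give 34/46 = 73.9% against a true 80.4%. It should therefore be reported beside the main estimate, not in its place.

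The cost is a short amendment and a few extra vital-status contacts, which can follow the 12-weekly timetable already in Section 9.5. Sample size, dosing and the primary analysis do not change. The amendment is best made while patients are still in follow-up, because event data not collected at the time may be impossible to recover later.

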## **7 TOXICITIES AND DOSE MODIFICATION**

Every effort should be made to administer the investigational product at the planned dose and schedule. In the event of study treatment toxicity, dosing may be interrupted, delayed, and/or reduced, as described in Section 7.4. In the event of multiple toxicities, treatment/dose modifications should be based on the worst toxicity observed (CTCAE v5.0) and/or the most conservative recommendation for any given toxicity. Patients are to be instructed to notify Investigators at the first occurrence of any adverse symptom.

All dose modifications must be clearly documented in the patient's medical chart and in the CRF. Appropriate follow-up assessments should be done until adequate recovery occurs as assessed by the Investigator.

### **7.1 Dose Modifications during the DLT period**

Dose reductions of itacitinib are not allowed during the DLT period unless a DLT has been confirmed for a specific patient. Dose reduction due to a drug-drug interaction (i.e. potent CYP3A4 inhibitors) will not be considered a DL, but these subjects will not be considered evaluable for DLT and will be replaced. If a subject experiences toxicity that meets DLT criteria during the DLT observation window, the patient should be taken off treatment. If the treating investigator feels that the patient is deriving clinical benefit, the patient may remain on study therapy only after discussion with and approval from the Principal Investigator.

After completion of the DLT observation period, dose modifications are allowed for patients who do not tolerate the protocol-specified itacitinib dosing to allow the patient to continue the study treatment. Dose modification guidelines are described below.

### **7.2 Dose Interruptions**

Dose interruptions for study treatment-related AEs are allowed as per the dose modification recommendations. Doses of any investigational product that were not administered due to toxicity will not be replaced within the same cycle. In addition to dose interruption, the need for a dose reduction at the time of treatment resumption should also be considered based on the dose modifications recommendations. Treatment with itacitinib may be delayed up to 2 weeks (14 days) to allow for the resolution of toxicity. Participants may resume treatment if no medical condition or other circumstance exists that, in the opinion of the investigator, would make the participant unsuitable for further participation in the study. The treating investigator should contact the Principal Investigator to discuss the case of any participant whose treatment has been delayed for more than 14 days before restarting treatment with itacitinib.

### **7.3 Dose Reductions**

Following dosing interruption due to treatment-related toxicity, the study drug may need to be resumed at a reduced dose as per the dose modification recommendations. Dose reduction should proceed by decreasing the administered dose by one dose level per Table 5.

Once the study treatment has been reduced for a given patient, all subsequent cycles should be administered at that dose level. Intra-patient dose re-escalation is not allowed.

**Table 5: Itacitinib Dose Levels**

Dose Level	Itacitinib
1	200 mg oral daily, Days 1-28 each cycle
-1	100 mg oral daily, Days 1-28 each cycle
-2	100 mg oral every other day, Days 1-28 each cycle

#### 7.4 Guidelines for Management of Adverse Events

After completion of the DLT period, patients experiencing adverse events attributed to itacitinib may undergo dose modifications for toxicity management. Since participants may enter the study with extensive pretreatment conditions and/or compromised bone marrow function, dose reduction recommendations provided in Table 6 are provided as guidelines. Individual decisions regarding dose modifications should be made using clinical judgment and an individual benefit/risk assessment taking into account relatedness of the AE to the study treatment and the participant's underlying condition. Adverse events that have a clear alternative explanation, or transient ( $\leq 72$  hours) abnormal laboratory values without associated clinically significant signs or symptoms, may be exempt from dose modification rules.

**Table 6: Adverse Event Management Guidelines**

ADVERSE EVENT	MANAGEMENT
Transaminitis	
AST and/or ALT $> 3.0 \times$ ULN if normal ALT/AST at baseline.	
 
1. Interrupt for up to 14 days until the toxicity has resolved to <math>\leq</math> Grade 1.
 
2. Restart at the previous dose. If assessed as related to itacitinib, restart at the next lower dose and monitor as clinically indicated. NOTE: In participants with GVHD-related chemistry elevations at baseline, contact the sponsor to discuss clinical management and possible dose reductions.
 

Total bilirubin elevations that occur in the presence of GVHD response that cannot be attributed to new liver GVHD or concomitant therapy.	
Total bilirubin 3.0-5.0 <math>\times</math> ULN:
 
 
• Repeat assessment within 7 days. If elevation persists: 
 
○ Reduce dose by 1 level until bilirubin <math>\leq 1.5 \times</math> ULN.
 
 
 

ADVERSE EVENT	MANAGEMENT
	
 
○ Resume the previous dose if resolved in 14 days; if > 14 days, maintain a reduced dose.
 
 
Total bilirubin > 5.0-10.0 × ULN:
 
 
● Repeat assessment within 7 days. If elevation persists: 
 
○ Interrupt until bilirubin ≤ 1.5 × ULN.
 
○ Monitor LFTs weekly or more frequently as appropriate.
 
○ Resume the previous dose if resolved in 14 days; if > 14 days, resume at reduced dose.
 
 
 
 
Total bilirubin > 10.0 × ULN:
 
 
● Repeat assessment within 7 days. If elevation persists: 
 
○ Interrupt until bilirubin ≤ 1.5 × ULN.
 
○ Resume at reduced dose if resolved in 14 days; if > 14 days, discontinue treatment and monitor as appropriate.
 
 
 

Total bilirubin elevations that occur in participants with score ≥ 1 liver GVHD that cannot be attributed to worsening liver GVHD or concomitant therapy.	
Total bilirubin > 3.0 × ULN:
 
 
● Repeat assessment within 7 days. If elevation persists: 
 
○ Reduce dose by 1 dose level.
 
○ Resume previous dose if bilirubin ≤ 3.0 × ULN.
 
 
 

Neutropenia	
ANC < 0.5 × 10  /L, suspected as unrelated to study drug (e.g., GVHD, active cytomegalovirus viremia).	
 
● Reduce dose by 1 dose level.
 
● Monitor ANC count as clinically indicated.
 
● Resume the previous dose if the ANC count is ≥ 0.5 × 10^9/L for more than 7 days.
 

ANC < 0.5 × 10  /L, suspected as related to study drug.	
 
● Interrupt for up to 14 days.
 
● Monitor ANC count as clinically indicated.
 
● Resume at a reduced dose if the ANC count is ≥ 0.5 × 10^9/L for more than 7 days. If the ANC count remains at ≥ 0.5 × 10^9/L for more than 7 days after resuming treatment at a lower dose, the previous dose may be resumed.
 

Thrombocytopenia	
Platelet count < 10 × 10  /L or platelet count has decreased by ≥ 50% from baseline, suspected as unrelated to study drug.	
 
● Reduce dose by 1 dose level.
 
● Monitor platelet count as clinically indicated.
 

ADVERSE EVENT	MANAGEMENT
	
 
Resume at previous dose if platelet count returns to <math>\geq 20 \times 10^9/L</math> or recovers to within 75% of the baseline value for more than 7 days.
 

Platelet count $< 10 \times 10^9/L$ or platelet count has decreased by $\geq 50\%$ from baseline, suspected as related to study drug.	
 
Interrupt for up to 14 days.
 
Monitor platelet count as clinically indicated.
 
Resume at a reduced dose if platelet count returns to <math>\geq 20 \times 10^9/L</math> for more than 7 days or recovers to within 75% of the baseline value. If the platelet count remains stable for an additional 7 days, the previous dose may be resumed.
 

Other Non-hematologic toxicities	
Any Grade 1 or Grade 2 toxicity.	
 
Continue treatment and manage the toxicity.
 
Monitor as clinically indicated.
 

Any Grade 3 toxicity, not manageable by supportive care.	
 
Interrupt up to 14 days until toxicity resolves to <math>\leq</math> Grade 1.
 
Restart at the same dose; if assessed as related to itacitinib, restart at next lower dose and monitor as clinically indicated.
 

Any recurrent Grade 3 toxicity at 100 mg QOD dose.	Discontinue study treatment; follow-up per Protocol.
Grade 4	Discontinue study treatment; follow-up per Protocol.

